## Statistical Plan and Data Analysis

The randomized groups will be descriptively compared on baseline demographic and pain variables using descriptive statistics. In particular, groups will be considered well-balanced on a particular baseline variable if the standardized difference (difference in means or proportions divided by the pooled standard deviation) is less than  $\sqrt{2/n}$ , where  $n$  is the per-group sample size. The primary analysis will be modified intention-to-treat, in which all randomized subjects who received any of the study treatment will be included and retained in their respective treatment groups.

**Aim 1: Primary outcome.** We will assess the average causal effect of cryoneurolysis versus sham/placebo on phantom limb pain intensity (average pain over past 72 hours) at 4 months after the initial treatment using analysis of covariance to adjust for baseline pain intensity and any imbalanced baseline variables (see above). Results will be summarized as the least squares difference in means at 4 months and 95% confidence interval. Mean and standard deviation change from baseline intensity will also be summarized. Similar analyses will be conducted for the secondary outcomes of current/present, worst and least phantom pain, as well as average and worst residual limb pain.

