### **Secondary outcomes.**

**Aim 2a.** The randomized groups will be compared on the global measure of improvement (Patient Global Impression of Change Scale) at 4 months using the Mann-Whitney test. Proportional odds logistic regression will be used to adjust for any imbalanced baseline variables, as appropriate.

**Aim 2b.** The randomized groups will also be compared at 4 months on the seven measures of Brief Pain Inventory, which evaluate pain's interference with physical and emotional functioning. We will use a mixed effects multivariate model (random subject term, fixed treatment effect, unstructured correlation matrix) to first assess whether the treatment effect differs across the individual measures (i.e., treatment-measure interaction). In presence of an interaction, each measure will be evaluated univariably. Otherwise, an overall treatment effect will be estimated from the mixed effects model as the primary result for this aim.

**Aim 2c.** Analysis of covariance adjusting for baseline score will be used to assess the treatment effect of cryoneurolysis versus sham on depression at 4 months after randomization as measured by the Beck Depression Inventory.

**Blinding assessment.** To assess the quality of the subject blinding as to initial treatment assignment, we will ask each subject on Day 0 to speculate which treatment they received (actual or sham cryo). A Pearson's chi-square test will be used to compare the proportion of correct speculations in each treatment group.

For all analyses, alternative statistical methods will be used if the assumptions of the planned analyses are not met. For instance, t-tests or regression analyses on the change or percent change from baseline (depending on which is less correlated with baseline score) will be used instead of analysis of covariance when comparing groups on the 4-week outcomes if the treatment group-by-baseline interaction is significant. Transformations of the data or Mann-Whitney test or other non-parametric procedures will be used if the assumptions of normality and/or equal variances are not met.

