**Sample size considerations.** Our sample size estimate is based on the primary specific aim of whether the addition of cryoneurolysis decreases phantom limb pain intensity resulting from an amputation compared with current standard-of-care treatment at 4 months following cryoneurolysis. Receiver operating characteristic curve analyses demonstrate that changes from baseline of at least 1.7 along a 10-point NRS accurately identified patients who rated improvements as “much improved” or more, compared with those who perceived no change or worsening following analgesic interventions. Multiple additional studies confirm this degree of reduction as clinically meaningful to individual patients with chronic pain. Meaningful group differences in the mean change would be somewhat smaller than important changes for individuals.

Therefore, we power our study to be able to detect group differences in mean change from baseline of 1.7 points or more on the NRS. Based on a conservative standard deviation estimate for each group of 3.0 at 4 months, a correlation of 0.50 between baseline and follow-up NRS, a two-sided test at the 0.05 significance level, power of 0.90, and 4 equally spaced analyses (3 interim and 1 final, as needed), a maximum of 72 subjects in each group (N=144 total) is required (East 5.3 software, Cytel Inc). The expected sample size for this group sequential design (i.e., average sample size over thousands of such trials, stopping when a boundary is crossed) is a total of 100 under the alternative and 102 under the null hypotheses. **Table 2** reports boundary crossing probabilities at each of the 4 analyses for this design, assuming that either the null or alternative hypotheses were true. For example, there is a cumulative 8%, 37% and 75% chance of crossing a boundary at the 1st, 2nd and 3rd analyses, respectively, if the alternative hypothesis were true. However, if the true standard

deviation at 4 months were smaller, say 2.5 instead of 3.0, then the cumulative probability of stopping for efficacy at the 1st, 2nd and 3rd analyses, respectively, would increase to 16%, 55% and 88% under the alternative hypothesis.

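### Undefined, data-driven triggers can replace the primary ANCOVA at any of the four looks, so the primary test and its scale are not fixed in advance

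*Combined protocol and SAP*

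**What the plan says.** Under Aim 1 (Statistical Plan and Data Analysis), the primary analysis is an ANCOVA of average phantom pain at 4 months, adjusted for baseline pain and any imbalanced baseline variables. "Results will be summarized as the least squares difference in means at 4 months and 95% confidence interval".

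The paragraph on alternative methods stands under Secondary outcomes, but its opening sentence reaches Aim 1: "For all analyses, alternative statistical methods will be used if the assumptions of the planned analyses are not met". It then gives two triggers.

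- **Interaction.** The replacement is "t-tests or regression analyses on the change or percent change from baseline (depending on which is less correlated with baseline score"). These "will be used instead of analysis of covariance when comparing groups on the 4-week outcomes if the treatment group-by-baseline interaction is significant".
- **Distribution.** Transformations of the data, or a "Mann-Whitney test or other non-parametric procedures will be used if the assumptions of normality and/or equal variances are not met".

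The paragraph does not give a significance level for the interaction, a test or cut-off for normality or variance, or an order for the checks. It does not say whether the fallback regression keeps baseline as a covariate, or whether the method is chosen once or afresh at each look.

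The sample size section assumes "a two-sided test at the 0.05 significance level, power of 0.90, and 4 equally spaced analyses (3 interim and 1 final, as needed". The Interim analyses paragraph and Table 2 give one set of P-value boundaries, at 36, 72, 108 and 144 patients.

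**The concern.** The primary test is named, but conditions judged on the trial's own outcome data can displace it. The replacements do not share a scale. Change stays in NRS points, percent change does not, and a rank test gives no mean difference. Only a result in points matches the promised summary and the 1.7-point difference on which the trial is sized.

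Aim 1 is tested up to four times against fixed efficacy and futility boundaries, and it is the first gate for Aims 2a to 2c. If a trigger fires at one look and not the next, successive looks use different statistics, and a decision to stop or continue could turn on which test was selected. Because the triggers are undefined, someone must decide after seeing data whether they have fired.

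The first fallback is also a doubtful remedy for the problem that invokes it.

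**Working it through.** **1. The plan's own figure.** Inputs from Sample size considerations: difference 1.7, SD 3.0 at 4 months, correlation r = 0.50, two-sided 0.05, power 0.90, four looks. Gamma spending of -4 (efficacy) and -2 (futility) comes from Interim analyses. A fixed design with SD 3.0 needs 66 per arm. The four-look design needs 71.8, so 72 per arm, with 90.1% power at 72. The efficacy P-values reproduce as 0.0016, 0.0048, 0.0147 and 0.0440. The stated N therefore fits a working SD of 3.0: an unadjusted analysis, or a change score if the baseline SD is also 3.0, since 3.0 × √(2 × (1 − 0.5)) = 3.0. With the ANCOVA residual SD, 3.0 × √(1 − 0.25) = 2.598, power at 72 per arm is 96.1%.

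**2. Does change cure an interaction?** Let arm k have mean a_k + b_k·X at baseline X. The mean change is a_k + (b_k − 1)·X. The slope difference is (b_1 − 1) − (b_0 − 1) = b_1 − b_0, exactly as before. In simulation the interaction P-values for the 4-month score and for change differed by no more than about 1e-13.

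If the fallback regression keeps baseline, then Y − X = a + τ·T + (β − 1)·X, and τ is the ANCOVA treatment effect. The switch then changes nothing.

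**3. Does percent change cure it?** Sometimes. In 3,000 simulated trials per case, with 0-10 integer scores and 72 per arm:

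| Assumed truth | Interaction P < 0.05, 4-month score | Same, percent change | Non-significant on percent change, given trigger |
|---|---|---|---|
| Proportional effect | 23% | 5% | 94% |
| Unequal slopes | 57% | 14% | 76% |

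Where no interaction was built in, the last figure was 26% to 57%.

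**4. Cost of using change.** Variance ratio to ANCOVA = (s1² + s0² − 2·r·s0·s1) / (s1²·(1 − r²)), with s1 = 3.0 and r = 0.5, so the denominator is 6.75. The documents give no baseline SD s0. Eligibility requires an NRS of at least 3, which suggests a narrower spread at baseline; a uniform 3-10 score has SD 2.29. Power is for one test at 0.044 with 72 per arm; ANCOVA has about 97% throughout.

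| s0 | Numerator | Ratio | Power of change |
|---|---|---|---|
| 1.5 | 9 + 2.25 − 4.5 = 6.75 | 1.00 | 97.1% |
| 2.0 | 9 + 4 − 6 = 7.00 | 1.04 | 96.6% |
| 2.29 | 9 + 5.24 − 6.87 = 7.37 | 1.09 | 95.7% |
| 3.0 | 9 + 9 − 9 = 9.00 | 1.33 | 91.3% |

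**5. Cost of raw Mann-Whitney, against ANCOVA.** The score distributions are assumed.

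| Setting | ANCOVA | Mann-Whitney |
|---|---|---|
| Four looks, bivariate normal, shift 1.7 | 95.8% | 88.3% |
| Four looks, integer NRS, shift 1.7 | 95.4% | 88.5% |
| One test at 0.044, integer NRS, shift 1.7 | 96.3% | 89.7% |
| One test at 0.044, 37% of treated patients at NRS 0-1 | 95.2% | 93.0% |

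A separate integer-score check under a shift gave about 97% and 92%.

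**6. The rule over four looks.** Assumptions, because the plan is silent: triggers at 0.05, interaction checked before normality, t-test as the fallback for an interaction, Mann-Whitney as the fallback for non-normality; 2,500 trials per scenario.

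- The method differed between at least two looks in 11-13% of trials with the interaction trigger alone, and in 24-37% with the normality check added.
- Type I error of the rule followed mechanically was 0.039 to 0.043.
- If the smallest of the four P-values (ANCOVA, change, percent change, Mann-Whitney) could be taken at each look, it was 0.085 to 0.118.

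Monte Carlo error is about 0.4 points for type I error and 0.4 to 1.0 points for power.

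**The case against.** ANCOVA is already the named primary analysis, and the alternatives are conditional. The choice between change and percent change follows a stated rule. Statisticians stay masked until the analysis is complete. All of this is true and limits the point.

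A reader might infer four stronger things that the documents do not support.

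- **That the switch inflates type I error.** Mechanical use showed no inflation. The 0.085 to 0.118 range requires free choice among P-values, which the plan does not authorise. Masking restrains such choice only partly, because two-sided P-values from coded groups can be compared without knowing which arm is active.
- **That the fallback never cures the interaction and always drops baseline.** This is exact for raw change but not for percent change. The text also permits regression, which may keep baseline, and lists transformations and other non-parametric methods beside Mann-Whitney.
- **That power falls from 96% to 90%.** This needs a baseline SD of 3.0, which the plan does not state. Even then, 90% is the power the trial was designed for, so what is lost is surplus.
- **That the distribution trigger would fire in most trials.** A simulated rate of 86% rests on Shapiro and Levene checks at 0.05 and on 37% near-complete responders. The plan names neither test, and the pilot in the Progress Report had 3 of 5 at NRS 1 or below. The rate is illustrative.

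The trigger sentence also names 4-week outcomes. Read literally it governs no planned ANCOVA, since those are all at 4 months. It is probably a slip, but the two must be reconciled.

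**Conclusion.** The point stands. The primary test and its scale depend on undefined checks of the trial's own data and may change between looks, while the boundaries and the 1.7-point sizing presume one analysis. Raw change leaves a slope difference exactly as it was. Percent change may remove it at the price of a different estimand, and baseline-adjusted regression on change is the ANCOVA again.

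The main costs are an unfixed estimand and room for discretion. The power cost is secondary: 0 to about 1.5 points for change at baseline SDs of 1.5 to 2.3, about 6 points at 3.0, and roughly 2 to 7 points for raw Mann-Whitney (7.5 in the bivariate normal run). These figures rest on r = 0.50, a 4-month SD near 3.0, 72 per arm and assumed score distributions.

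Nothing found makes the switch necessary. ANCOVA held its type I error at 72 per arm on integer scores (0.041 at nominal 0.044), as did the version with HC3 standard errors (0.038).

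**What to change.** State that the primary analysis at all four looks is ANCOVA of month-4 average phantom NRS on treatment and baseline NRS, plus the other covariates that Aim 1 provides for unless those are changed separately. Use heteroscedasticity-robust standard errors, for example HC3 with a t reference distribution, and report the mean difference whatever the assumption checks show. Name the reference distribution: at the first look (18 per arm, boundary 0.0016) simulated HC3 type I error was 0.0012 with t but 0.0026 with the normal.

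Report the interaction model with centred baseline, and the change, percent-change, transformed and rank analyses, as sensitivity analyses only. Correct or explain the 4-week wording against the 4-month endpoint.

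The cost is SAP wording, with no change to sample size, boundaries or data collection. The one downside is that a rank or transformed analysis can no longer become primary.

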**Optional crossover treatment.** Four to six months following the initial treatment, subjects **may** return for an optional repeated intervention procedure (“crossover”) with the alternative treatment (either active cryoneurolysis or sham/placebo), again in a double-masked fashion using the same protocol as described for the initial intervention. **The crossover treatment is not required for study participation, as the primary analyses will include a parallel study design for the initial intervention evaluated prior to any crossover treatment.** However, an optional crossover treatment will be offered to subjects for two reasons: (1) it will ensure that all subjects have access to the proposed treatment, regardless of the treatment they are initially randomized to; and, (2) it will permit intra-subject differences between treatments to be analyzed (e.g., assessing treatment-effect heterogeneity, or the variability of the causal effect across individuals, which would not be available from the parallel-group portion of the study alone). These intra-subject differences will be secondary analyses, as there may be patient-selection bias regarding which subjects decide to have the crossover treatment (e.g., if the intervention is successful at greatly reducing phantom limb pain, then subjects receiving active cryoneurolysis during their initial treatment will be more likely to forgo the crossover treatment). This crossover will **not** affect the primary analyses, which will involve a parallel group study design and investigate the effects of cryoneurolysis within 4 months of the initial intervention. The approximate duration of a crossover visit will total 2-4 hours, from the time the subject enters the treatment facility until the time the depart.

Following study completion, the results will be mailed to all enrolled subjects in written form using non-technical (i.e. “layperson”) language.

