**Table 1. Summary of post-enrollment assessments.**

Subjects:	All							Participating in Crossover *							All
Time Point Following:	Initial Treatment							Crossover Treatment							Initial
Time Point (Days):	0	1	7					0	1	7					
Time Point (Months):			1		2	3	4			1		2	3	4	12
Brief Pain Inventory (for Phantom Limb Pain)	•	•	•	•	•	•	•	•	•	•	•	•	•	•	•
Residual Limb Pain (NRS)	•	•	•	•	•	•	•	•	•	•	•	•	•	•	•
Patient Global Impression of Change Scale	•	•	•	•	•	•	•	•	•	•	•	•	•	•	•
Beck Depression Inventory	•							•							•
Non-Painful Phantom Sensations	•	•	•	•	•	•	•	•	•	•	•	•	•	•	•
Phantom Limb Pain	•	•	•	•	•	•	•	•	•	•	•	•	•	•	•
Residual Limb Pain	•	•	•	•	•	•	•	•	•	•	•	•	•	•	•

\* The second—or “crossover”—treatment intervention will occur between 4-6 months following the initial treatment

**Demographic and amputation history.** Subjects will have demographic data collected, including

age, sex, height, weight, educational level, employment status, marital status, current analgesic regimen (including adjuvants such as acupuncture), and U.S. military service (e.g., none, discharged, active). In addition, amputation-specific data will include date of initial amputation, date(s) of subsequent surgical procedures, amputation etiology, amputation level, other amputations (with dates/etiology/pain), and prosthesis use.

**Hypothesis 1:** Phantom limb pain **intensity** will be significantly decreased 4 months following one cryoneurolysis procedure (as measured by the Numeric Rating Scale within the Brief Pain Inventory).

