**Crossover phase.** Beginning 4-6 months after the original randomization, requesting subjects will receive the opposite treatment from that received in their original randomization, and the same measurements will be collected through 4 months (see **Table 1**). This option will allow all subjects the opportunity to receive the study treatment. Although a completely unbiased assessment of the average causal effect will not be possible for this phase because the second treatment will be

[figure not shown]
voluntary, and crossover will thus likely be requested more often from those receiving sham/placebo in the first phase, we will still descriptively report the average treatment effect from those choosing to cross over (but no testing will be done; unbiased average causal effect will be obtained from the first phase).

More importantly, we will estimate the variability in the individual causal effects of cryoneurolysis versus sham/placebo using this crossover design. Variability of the individual causal effects cannot be directly estimated in a parallel group study (e.g., from the main portion (Aim 1) of this study we can only directly estimate the average causal effect), since only the outcome for the single treatment received is measurable for each subject. However, estimation of the variability of the individual causal effects from the crossover study, quantified as the standard deviation of within-subject differences on treatment versus sham/placebo, will provide valuable information about the heterogeneity of the treatment effect across subjects associated with cryoneurolysis treatment of phantom limb pain. We will also use regression models to explore whether any baseline factors are associated with higher or lower causal effects of treatment.

**Long-term follow-up.** Data for all outcomes will also be collected at 12 months post randomization. Due to the crossover design, we will not be able to directly assess the treatment effect of cryoneurolysis versus sham on these outcomes. Rather, we will descriptively assess the change from the initial baseline to 12 months for various groups of subjects: 1) all who received the active treatment either initially or in the crossover, 2) initial control subjects who were not crossed over; 3) initial control subjects who were crossed over; 4) initial treated subjects who were not crossed over; 5) initial treated subjects who were crossed over.

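### The crossover analysis reports the SD of within-subject differences as variability of individual causal effects, but with one period per treatment that SD also contains period-to-period pain fluctuation

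*Combined protocol and SAP*

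**What the plan says.** The Optional crossover treatment paragraph (section 9) gives two reasons for offering the second treatment. The second reason is to study differences within subjects, for example "assessing treatment-effect heterogeneity, or the variability of the causal effect across individuals". It adds that "These intra-subject differences will be secondary analyses", because crossing over is voluntary.

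The Crossover phase paragraph of the statistical plan makes this operational: "we will estimate the variability in the individual causal effects of cryoneurolysis versus sham/placebo using this crossover design". The measure is "quantified as the standard deviation of within-subject differences on treatment versus sham/placebo". The paragraph contrasts this with the parallel phase, which it says can directly estimate only the average effect.

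A subject who crosses receives the opposite treatment once. According to the footnote to Table 1, the second "treatment intervention will occur between 4-6 months following the initial treatment". On timing of the readings the Crossover phase paragraph says only that "the same measurements will be collected through 4 months". It does not say which reading in each period forms the difference.

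The limitation discussed in both paragraphs is selective participation, for example that "subjects receiving active cryoneurolysis during their initial treatment will be more likely to forgo the crossover treatment". Neither mentions fluctuation between periods or carryover.

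**The concern.** A difference between one active reading and one sham reading is the subject's individual effect plus whatever else changed in that subject's pain between the two occasions. With no repeated period on either treatment, these parts cannot be separated from the differences alone. The spread of the differences is above zero even when every patient benefits equally, unless pain is otherwise perfectly stable.

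What is at stake is interpretation. A large SD would be read as showing that some patients benefit greatly and others little or not at all, when much of it, or all of it, could be ordinary variation in pain scores. The plan introduces this analysis as more important than the descriptive average from the crossover, so the number is likely to be reported and relied on.

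**Working it through.** **Inputs from the plan (Sample size considerations).** SD of the NRS at 4 months 3.0 per group, with 2.5 as an alternative; correlation 0.50 between baseline and follow-up; target difference 1.7; 72 per group.

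**Check on those inputs.** The plan gives no value for the SD of within-subject differences, so the nearest figure to reproduce is N = 144. The SD of change is sqrt(2 × 3.0² × (1 − 0.50)) = 3.0. A fixed design at two-sided 0.05 and power 0.90 needs 65.44 per arm before rounding. Four looks with gamma(−4) efficacy and gamma(−2) non-binding futility spending inflate this by 1.093: 2 × 65.44 × 1.093 = 143.0, which rounds up to 144 in equal groups. The inputs are therefore read as the plan uses them.

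**Model.** Let D be the active-minus-sham difference, tau the SD of the true individual effects, s the per-period SD apart from effect variation, and r the correlation between the two periods. With no carryover, and fluctuation independent of the individual effect:

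SD(D) = sqrt(tau² + 2s²(1 − r)).

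The plan gives no r for two readings 4-6 months apart. Its 0.50 is for baseline against follow-up. So r is assumed and shown over a range.

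**Identical effect in everyone (tau = 0).**

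| r (assumed) | SD(D), s = 3.0 | SD(D), s = 2.5 |
|---|---|---|
| 0.3 | 3.55 | 2.96 |
| 0.5 | 3.00 | 2.50 |
| 0.7 | 2.32 | 1.94 |
| 0.8 | 1.90 | 1.58 |
| 0.9 | 1.34 | 1.12 |

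Only r = 1 gives zero. At s = 3.0 and r = 0.5, the share of subjects who would appear worse on active, although all gain exactly 1.7, is Φ(−1.7/3.0), about 28%.

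**Sensitivity to real heterogeneity.** At s = 3.0 and r = 0.5, raising tau from 0 to 1.0 moves SD(D) from 3.00 to sqrt(1 + 9) = 3.16; tau = 2.0 gives sqrt(4 + 9) = 3.61.

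**Reading backwards.** Suppose SD(D) = 2.5 is observed and s = 3.0. Then tau = sqrt(6.25 − 18(1 − r)), which is 0, 0.92, 1.63 or 2.11 for r = 0.65, 0.7, 0.8 or 0.9.

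**Active-first crossers.** If an assumed fraction k of each subject's effect persists into the sham period, that part cancels from the difference: SD(D) = sqrt((1 − k)²tau² + 2s²(1 − r)). With assumed tau = 2, r = 0.9 and s = 3.0 this is sqrt(1.8) = 1.34 for k = 1 and sqrt(1 + 1.8) = 1.67 for k = 0.5. Both are below the true tau, so the SD is not an upper bound in that sequence.

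**Does the bound hold for sham-first crossers?** Usually, but not always. A simulation assumed a sham mean of 6, s = 3.0, scores rounded and limited to 0-10, and crossing when the sham score is 4 or more. Relief was proportional to pain: 60% of subjects with full relief, the rest with a 29% or 57% reduction, loosely following the pilot in the Progress report. At r = 0.5, SD(D) was 2.73 against a true effect SD of 2.83. With additive effects, tau = 3 and r = 0.9, the scale limits alone brought SD(D) to 2.80.

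**The case against.** The strongest reply is that this is a secondary, untested description. It has no hypothesis in the Specific Aims and lies outside the gatekeeping order. The plan promises only useful information on heterogeneity and already warns about selective crossover. That limits the consequence but does not correct the label: the existing warnings concern who crosses, not what the SD contains.

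A second reply is that r is assumed and the trial's own data would narrow it. Sham-first crossers have repeated readings under sham and a second Day 0 reading, and controls who do not cross have a Month 12 reading. This is fair, although placebo response and selection at entry would make such estimates imperfect. The plan does not propose to use them for this purpose.

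A third reply concerns carryover. The Background describes a conduction block of 6-8 weeks with full recovery, which would be over before a crossover at 4-6 months, and most crossers are expected to be sham-first. This stands as a reason not to treat carryover as established. However, the Progress report and Potential benefits sections hope for lasting or permanent relief, so it cannot be ruled out for active-first subjects.

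A reader might also infer that the SD says nothing about heterogeneity, or that the planned regressions on baseline factors fail for the same reason. Neither follows. The SD can serve as an approximate upper bound in sham-first crossers, and noise in the differences does not invalidate regressions on measured factors.

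**Conclusion.** The concern holds as a mislabelled estimand. The planned SD is total within-subject variability: effect heterogeneity plus occasion-to-occasion fluctuation. With no carryover and fluctuation independent of the effect, it overstates heterogeneity by an unquantified amount. At a per-period SD of 3.0 it reads between 1.34 and 3.55 points under zero heterogeneity for assumed r from 0.9 to 0.3, and at r of 0.8 or below this exceeds the 1.7-point target effect. The direction and existence of the problem hold for every r below 1 under those two conditions; the size depends on r, which the plan does not state.

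A reader might take 0.50 as the between-period correlation and quote 3.0 as the size of the error. The documents do not support that, because the 0.50 refers to baseline and follow-up. Nor do they support any doubt about the primary result: the randomised first-phase comparison does not use these differences. The change should be made before analysis, but it is a matter of interpretation in a secondary analysis.

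**What to change.** In the Crossover phase paragraph, and in the purpose given under Optional crossover treatment:

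- Describe the SD as total within-subject variability (effect heterogeneity plus occasion-to-occasion fluctuation), not as the variability of causal effects.
- Specify that the difference uses the 4-month score in each period.
- Report the SD separately for sham-first and active-first crossers.
- For sham-first crossers only, allow it to be described as an approximate upper bound on heterogeneity. State the assumption that fluctuation is independent of the individual effect, and note that this can fail if relief is proportional to pain or scores reach the limits of the 0-10 scale.
- Do not give that reading to active-first crossers, whose sham period may carry treatment effect if relief persists.

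The cost is wording and a little analysis time, with no new visits, subjects or data. The price is a weaker statement about heterogeneity and an imprecise active-first SD if few of that group cross. With an assumed 6 or 12 such subjects, the normal-theory 95% limits, sqrt((n − 1)/chi-square quantile on n − 1 df), are 0.62 to 2.45 or 0.71 to 1.70 times the estimate.
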